#### Pharmacokinetics:

PK data collected in this study will be included in a population PK analysis of plasma concentrations of liafensine and its primary metabolite. It will be performed using a nonlinear mixed-effects modeling approach. The analysis will evaluate the effects of age, sex, ethnicity, and other covariates on the PK profile of liafensine. The results of this analysis with be reported separately.

#### Statistical Analysis Plan:

Additional details of the analyses will be provided in the statistical analysis plan which will be finalized prior to unblinding.

#### **Ethical Considerations:**

This study will be conducted in accordance with applicable country-specific laws and regulations, including, but not limited to, International Council for Harmonisation of Technical Requirements for Pharmaceuticals for Human Use (ICH) Good Clinical Practice (GCP) guidelines and the ethical principles that have their origins in the Declaration of Helsinki. The institutional review board (IRB)/independent ethics committee (IEC) must review and approve the protocol and ICF before any patients are enrolled. Before any procedures specified in the protocol are performed, the patient must sign and date the IRB/IEC-approved ICFs.

**Table 1:** Schedule of Assessments

Screening 1   Screening 2			Baseline		Doub	le-Blind Tre	eatment		Follow-upb	
Study Procedures a	Visit 1	Visit 2 °	Visit 3	(No visit)	Visit 4	Visit 5	Visit 6	Visit 7 EOT	14 days post-last dose	28 days post-last dose
	Prior to Day -21	Day -21 to Day -2 d	Day -1e	Day 1e	Day 7	Day 14	Day 28	Day 42 f		
Visit window (day)			+ 3		± 3	± 3	± 3	± 3	± 3	± 3
Brief informed consent	$X^{g}$									
Full informed consent g		$X^{g}$								
Preliminary Inclusion/exclusion	$X^h$									
Inclusion/exclusion		X	X							
Medical/surgical history	X									
Prior medications		X								
Demographics	X									
Psychiatric evaluation via MINI (selected or full modules)		X								
ATRQ (5 Year)		X								
Physical examination		X						X		
Neurological examination		X						X		
Blood sampling for PGx i	X					X				
Randomization			X							
Study drug dispensing			X		X	X	X			
Study treatment				X				X		
MADRS rater 1		X	X		X	X	X	X		
HAMD-17 rater 1		X	X							
SDS			X					X		
PRPS			X							
PRDF Checklist j		X	X		X	X	X	X		
CGI-S rater 2		X	X		X	X	X	X		
CGI-I rater 2					X	X	X	X		
C-SSRS		X k	X l		X l	X l	X l	X l	X l	X l
DESS m									X	

	Screening 1	Screening 2	Baseline	Follo	w-up b					
Study Procedures a	Visit 1	Visit 2 °	Visit 3	(No visit)	Visit 4	Visit 5	Visit 6	Visit 7 EOT	14 days	28 days
	Prior to Day -21	Day -21 to Day -2 d	Day -1 e	Day 1e	Day 7	Day 14	Day 28	Day 42 f	post-last dose	post-last dose
Visit window (day)			+ 3		± 3	± 3	± 3	± 3	± 3	± 3
Vital signs n		X	X		X	X	X	X	X	
Body weight		X						X		
Height		X								
12-lead ECG o		X	X					X		
Clinical laboratory tests p		X	Xq			X	X	X	X	
Urinalysis (on-site/central labs in the event of macroscopic findings)		X	$X^q$					X		
Urine drug screen (on-site)		X	$X^q$					X		
Pregnancy test r	X		X					X		
Blood sampling for PK s							X	X		
Concomitant medications			X							X
Collection of AEs	X									X

Abbreviations: AE = adverse event; ATRQ = Antidepressant Treatment Response Questionnaire; BP = blood pressure; CGI-I = Clinical Global Impressions—Improvement Scale; CGI-S = Clinical Global Impressions—Severity Scale; C-SSRS = Columbia—Suicide Severity Rating Scale; DESS = Discontinuation—Emergent Signs and Symptoms scale; ECG = electrocardiogram; EOT = End-of-Treatment; FT3 = free triiodothyronine; FT4 = free thyroxine; HAMD-17 = Hamilton Depression Rating Scale - 17 Item; HIV = human immunodeficiency virus; MADRS = Montgomery-Åsberg Depression Rating Scale; MINI = Mini International Neuropsychiatric Interview; PGx = pharmacogenomics; PK = pharmacokinetics; PRDF Checklist = Patient Rated Depression and Functioning Checklist; SAE = serious adverse event; PRPS = Placebo Response Propensity Scale; SDS = Sheehan Disability Scale; TSH = thyroid-stimulating hormone

- a Every effort should be made for visits to occur on the designated study days. A ± 3-day visit window is permitted at all visits except for Screening and Baseline (Day -1). The overall treatment period in the protocol should be maintained (ie, visits should be scheduled based on the baseline visit rather than the previous visit). Study procedures designated for a specific visit should be performed on 1 day whenever this is possible and in the best interest of the patient. If this is not possible and/or not in the best interest of the patient, study procedures may be performed across more than 1 day but within the visit window.
- b Randomized patients who complete the study or discontinue early will have two follow-up visits (14 and 28 days after the last dose of study drug), the 2nd follow-up visit will be conducted via phone call.
- c Visit 2 activities are performed only after the confirmation of initial eligibility including PGx. Patients who screen fail due to PGx status are not eligible for rescreening.

Prior to	Day -21 to	Day -1e	Day 1e	Day 7	Day 14	Day 28	Day 42 f	
Day -21	Day -2 a	=	_			•	-	

d Screening period may exceed 20 days if a prolonged washout is required.

- e Baseline evaluations will be performed on Day -1. Patients will be instructed to take the first dose of double-blind study drug the day after baseline evaluations (ie, on Day 1), and will be instructed to take double-blind study drug for the remainder of the 6-week treatment period.
- f For patients who discontinue early from the study, safety and efficacy determinations designated for Day 42 will be performed on the last day the patient takes a full dose of study drug or as soon as possible thereafter, but within 3 days of their last dose in any event.
- g At Visit 1, two brief ICFs will be obtained for the purpose of genotyping and biobanking, separately. A full ICF must be obtained at Visit 2.
- h Refer to Appendix 2 Preliminary Diagnosis Checklist
-  A separate blood sample (6 mL) will be collected for PGx (eg, determination of DGM4 status at Screening and for future research at Visit 5).
- The PRDF Checklist must be completed by the patient and reviewed by the rater 2 prior to CGI-S assessment. The baseline checklist entry must be compared by rater 2 against post-baseline entry to refresh the knowledge of patient's baseline condition prior to CGI-I assessment.
- k C-SSRS baseline/screening version
-  C-SSRS since-last-visit version
- m For randomized patients who complete the study or discontinue early, the DESS scale will be completed daily by the patient for 14 days post-last dose.
- n Vital signs should be taken prior to blood draws when applicable and include supine (after at least 5 min rest) and standing (after 1 min and 3 min standing), BP and heart rate, respiration rate, and temperature. Vital signs can be repeated for up to 3 occurrences after Visit 2 to see if values return to normal range, but any abnormality must be resolved by the Baseline Visit.
- o ECG recordings will be completed prior to blood draws when applicable and will be performed in triplicate (at 1-minute intervals between each of the three recordings) for baseline. Single ECG will be performed for rest of the timepoints.
- P Hematology, blood chemistry, and urinalysis will be performed at all visits with a laboratory determination. Serologic tests for HIV, hepatitis B core antibody, hepatitis B surface antigen, and hepatitis C virus antibody, and a thyroid panel (TSH, FT3, and FT4) will be completed only at Screening. Laboratory tests can be repeated for up to 3 occurrences after Visit 2 to see if values return to normal range, but any abnormality must be resolved by the Baseline Visit.
- q To be conducted on Day -1 only if (1) the screening period exceeds 21 days; (2) a longer than 21-day prior medication washout is required, eg, fluoxetine > 20 mg/day; (3) per investigator's judgement. For women of pre-menopause, an inquiry of menses status should be made in the presence of macroscopic blood detection before submitting the sample to the central labs for microscopic examination.
- r Serum pregnancy testing will be performed in females of childbearing potential at Screening 1 and Day 42 (Visit 7). Urine pregnancy testing will be performed at Baseline (Day -1, dip stick).
- s Blood samples for PK will be collected on Day 28 (Visit 6) and on Day 42 (Visit 7) prior to dose administration, or at the time of early withdrawal, if within 3 days of last dose. Time of last dose and time of blood collection will be recorded. When possible, and if medically appropriate, blood samples should be collected for PK from patients who experience an SAE or overdose.

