#### **Study Design:**

This study will be conducted as a multicenter, randomized, double-blind, placebo-controlled Phase 2b trial to assess the efficacy, safety, tolerability, and PK of liafensine in DGM4-stratified TRD patients. The study includes an up to 21-day screening period.

Approximately 180 patients with TRD who meet all eligibility criteria will be randomized in a 1:1:1 ratio to receive either liafensine 1 mg QD, liafensine 2 mg QD, or placebo QD for 6 weeks. Approximately 150 randomized patients carrying genotype GG at DGM4 (DGM4-positive) and approximately 30 randomized patients carrying genotype AA or AG at DGM4 (DGM4-negative) will be enrolled in this study. DGM4 status (positive vs negative) of randomized patients will be blinded to the sites, the patients, and sponsor. An Interactive Response Technology (IRT) system will be used for blinding DGM4 status, and to achieve the planned randomization ratio of DGM4-positive:DGM4-negative patients by randomly excluding most screened DGM4-negative patients (~80%). Randomization will be stratified by DGM4 status (positive vs negative) and region (North America vs Other). Patients who complete the study or discontinue after randomization will have two post-study follow-up visits (14 days after the last administered dose of study drug, and 28 days after the last administered dose of study drug); the 2nd follow-up visit will be conducted via phone call. Every effort will be made to ensure that the protocol-required tests and procedures are completed.

During the study, safety will be assessed on the basis of spontaneously reported AEs; the DESS; physical, neurological, and psychiatric examinations (including the C-SSRS); vital signs including supine and standing blood pressure and heart rate; weight; 12-lead ECGs; clinical laboratory test results; serum and urine pregnancy tests (females of childbearing potential only); and concomitant medication assessments. In addition to blood samples collected for PK, additional blood samples may be collected for determination of plasma concentrations of liafensine and its primary metabolite in association with the evaluation of safety signals.

The overall study design is shown in Figure 1. The schedule of study assessments is presented in Table 1 with the clinical laboratory tests shown in Table 3.

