#### 4.4.1. Withdrawal from Study Treatment or Study Participation

Patients must be discontinued from **study treatment** for any of the following reasons:

• Unacceptable toxicity in the opinion of treating investigator that the risk outweighs potential benefit for the subject. For laboratory abnormality meeting withdrawal criteria, please refer to Section 7.6.1.8.

Pregnancy

Patients may be discontinued from **study participation** for any of the following reasons:

- Intercurrent illness
- Withdrawal of consent
- Death
- Study terminated by the sponsor, relevant regulatory agencies, or institutional review board (IRB)/independent ethics committee (IEC)

All patients who discontinue from study treatment are encouraged to continue the study participation, and at a minimum undergo the End-of-Treatment (EOT) assessments, unless consent is withdrawn, as indicated in the schedule of events (Table 1). If a patient does not return for a scheduled visit, every effort should be made to contact the patient.

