The same model in the primary analysis will be used without imputation using the treatment policy strategy per ICH E9(R1) (Polverejan 2023). This analysis will be used to assess the impact of imputing missing values based on the MAR assumption.

3. MMRM with imputation using pattern mixture model

This sensitivity estimator will be using a control-based multiple imputation method (Ratitch 2013). This sensitivity analysis does not rely on the MAR assumption. Data collected after initiation of prohibited medications will not be used unless otherwise specified. Missing data due to all ICEs will be handled per specifications below unless otherwise specified.

In this sensitivity analysis, imputation will be implemented using SAS MI procedure with FCS statement and REGPMM option, as well as MNAR statement with MODELOBS option to identify observations from the placebo arm for deriving the imputation models, ie, assuming all missing data will have a profile that equals the profile of the placebo arm for all time points. The variables to be used in the imputation are region, baseline values, and change from baseline values observed at Weeks 1, 2, 4, and 6.

One hundred fully imputed datasets will be created. The MMRM described in Section 5.4.1.2 will be used for treatment comparisons. Treatment effects (difference in LS means between treatment arms) from these 100 analyses will be combined to generate the final results using Rubin's method with SAS MIANALYZE procedure.

A tipping point analysis for this sensitivity analysis will also be conducted to assess the robustness of the result. The same steps described in the first sensitivity analysis will be followed.

4. Sensitivity Analyses based on RAS

A set of sensitivity analyses listed below will be performed using DGM4-positive patients in RAS. The same MMRM in the primary and sensitivity analyses described above will be carried out with the exclusion of the following fixed effect: treatment by baseline MADRS total score. In other words, the model will include the fixed effects of treatment, visit (categorical covariate), treatment by visit interaction, baseline MADRS total score (continuous covariate), and region.

The following analyses will be performed in this set of sensitivity analyses:

- 1) The primary analysis, as well as the 1st and 2nd sensitivity analyses based on FAS will be repeated using RAS.

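### No passage says which efficacy visits a patient who stops drug but stays in the study attends, so the analysis labelled treatment policy may have few or no off-drug scores

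*Protocol*

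**What the plan says.** - **Protocol 4.4.1** separates stopping treatment from leaving the study: "All patients who discontinue from study treatment are encouraged to continue the study participation, and at a minimum undergo the End-of-Treatment (EOT) assessments". It then refers to Table 1 for the schedule.
- **Table 1** lists MADRS and CGI-S at Screening 2, baseline, Days 7, 14 and 28, and Visit 7. Visit 7 is both EOT and Day 42. MADRS, CGI-S, CGI-I and SDS are blank in both follow-up columns.
- **Table 1, footnote b,** sets later contacts: "Randomized patients who complete the study or discontinue early will have two follow-up visits (14 and 28 days after the last dose of study drug". Of these, the second is a phone call.
- **Synopsis, Study Design:** "Patients who complete the study or discontinue after randomization will have two post-study follow-up visits". Protocol 3.1 and SAP 2.1 say much the same.
- **Table 1, footnote f:** "For patients who discontinue early from the study, safety and efficacy determinations designated for Day 42 will be performed on the last day" of full dosing or soon after, "but within 3 days of their last dose in any event".
- **SAP 3.4** assigns scores to visits by study day: Days 11–20 to Visit 5, 21–34 to Visit 6, 35–49 to Visit 7.
- **Protocol 8.3.2 and SAP 5.4.1.1** define a hypothetical primary estimand: the effect if patients had stayed on their treatment.
- **SAP 5.4.1.2** nevertheless keeps every available score in the main analysis, whether recorded before or after an intercurrent event.
- **SAP 5.4.1.3, item 2:** "The same model in the primary analysis will be used without imputation using the treatment policy strategy per ICH E9(R1").

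**The concern.** A treatment-policy analysis of treatment discontinuation needs scores taken after the drug was stopped. The protocol encourages patients to remain in the study, but gives the site no visit schedule for someone off drug and still participating. It does not say whether EOT and Day 42 then become two assessments, or how contacts counted from the last dose fit with visits counted from baseline.

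Two sites can therefore act reasonably and produce different data for the same kind of patient. One takes an early EOT score and then only safety contacts; the other continues MADRS to Day 42. Whether the primary time point is observed or missing then depends on how the site reads the protocol, and analysts cannot recover an uncollected Day 42 score. If most sites take the first course, a reader of the results would see an analysis called treatment policy that contains almost no information on patients after they stopped.

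**Working it through.** **1. The design figure.** Inputs (Protocol 3.4 and 8.2, SAP 2.3): difference 4.5, SD 9, 80% power, 2-sided 0.05, pooled active to placebo 2:1.

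n per arm = 1.5 × [9 × (1.960 + 0.842) / 4.5]² = 47.09, against 47 stated. Power at 47 vs 94 is 79.9%. The figure reproduces.

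Design standard error = 9 × √(1/47 + 1/94) = 1.61 points.

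**2. The passages side by side, for a patient who stops drug and does not withdraw consent.**
- 4.4.1: staying is encouraged; the minimum is EOT, as shown in Table 1.
- Table 1: EOT shares its column with Day 42, so completing EOT can be read as completing Visit 7.
- Footnote b and the synopsis: two contacts counted from the last dose, for anyone who discontinues. The synopsis calls them post-study.
- Footnote f: moves the Day 42 assessments to within 3 days of the last dose, but is worded for patients who leave the study.
- No passage lists the remaining MADRS and CGI-S visits for this patient.

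**3. Day arithmetic if efficacy assessment ends at an early EOT.** Let L be the day of the last dose. The latest EOT is L + 3; the contacts are at L + 14 and L + 28. SAP 3.4 windows are applied by study day.

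| L | Latest EOT | Contacts | EOT score can fall in Days 35–49? |
|---|---|---|---|
| 7 | 10 | 21, 35 | No |
| 13 | 16 | 27, 41 | No |
| 14 | 17 | 28, 42 | No |
| 28 | 31 | 42, 56 | No |
| 31 | 34 | 45, 59 | No |
| 32 | 35 | 46, 60 | Only if taken on the last permitted day |

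- L ≤ 31: 31 + 3 = 34, so no score reaches the Day 42 window.
- L ≤ 13: 13 + 28 = 41, so every contact is over before Day 42.
- L = 14: the contacts fall on Days 28 and 42, the nominal MADRS days, with no MADRS scheduled at them.
- L ≤ 35: 35 + 3 = 38, so EOT also misses the protocol's own Day 42 window (42 ± 3, Days 39–45).

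**4. What analysis 2 becomes.** Without post-stop scores it is an MMRM on scores taken on drug or within 3 days of the last dose. Later values are handled under missing at random (MAR), which is also the assumption behind the primary imputation.

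**5. Distance between the two estimands.** The documents give no discontinuation rate. The only allowance, about 5%, covers patients with no dose or no post-randomization evaluation. Assume a fraction d stops in each arm and keeps none of the benefit at Day 42:

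treatment-policy effect = 4.5 × (1 − d)

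| d | Effect | Gap from 4.5 | Gap / 1.61 |
|---|---|---|---|
| 10% | 4.05 | 0.45 | 0.28 |
| 15% | 3.83 | 0.68 | 0.42 |
| 20% | 3.60 | 0.90 | 0.56 |

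Partial retention of benefit would shrink the gap.

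**The case against.** The strongest reply is that the texts fit together. Footnote f is limited to patients leaving the study, and 4.4.1 covers those who only stop drug. Footnote b adds contacts without saying that they replace the remaining visits, and footnote a counts visits from baseline. Section 4.4.1 encourages rather than requires continuation and itself points to Table 1. The 3-day efficacy rule is in footnote f only; the synopsis prose has a 3-day limit just for the PK sample. All of this stands, and it is why the point is an ambiguity with a missing schedule rather than a contradiction. It does not supply the schedule.

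Three stronger readings are tempting, and the documents do not support them.
- **The primary effect is overstated by 0.45–0.90 points.** The primary estimand is hypothetical. Under the assumptions above, 4.5 is its target, so the gap is not an error in it.
- **The plan never tests what happens after a stop.** SAP 5.4.1.3 also has tipping-point analyses, control-based imputation that does not rely on MAR, and imputation by intercurrent event in the randomized set, with adverse-event stops imputed from placebo.
- **Off-drug scores would make analysis 2 an independent check.** Under SAP 5.4.1.2 the primary uses the same observed scores, so the two would track each other with or without them.

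Nor is a complete absence of off-drug data certain. Patients who accept the encouragement can supply scores, and the label has content for prohibited medication, which can begin while a patient is still on study drug.

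**Conclusion.** The point holds as a gap in the assessment schedule together with a label that the schedule does not support. If a site ends efficacy assessment at an early EOT, which is a reasonable reading, a last dose on Day 31 or earlier leaves no score in the SAP Day 42 window. For treatment discontinuation, analysis 2 may then have few or no off-drug scores and rests on MAR like the primary.

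The 0.45–0.90 point gap, about 0.3–0.6 of the design standard error, illustrates how far the two estimands may lie apart. It rests on an assumed 10–20% stopping rate, equal in all arms, with full loss of benefit. It is not an estimate for this trial.

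The primary is touched in a different way. Because it keeps post-event scores, any off-drug scores that sites do collect enter an analysis meant to target the on-drug effect. That conflict between estimand and data rule exists now and would grow with better collection.

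**What to change.** 1. Reconcile Protocol 4.4.1, the synopsis and 3.1, Table 1 footnotes b and f, and SAP 2.1. They should say the same thing about which scheduled MADRS and CGI-S assessments through nominal Day 42 apply to a patient who stops drug but remains in the study, and list these separately from the EOT assessment and the safety contacts.
2. In SAP 5.4.1.2, state how scores after treatment discontinuation are handled in the primary, so that it matches the hypothetical estimand. In 5.4.1.3 item 2, state that those scores are used. Without this step, collecting more off-drug scores would pull the primary towards treatment policy.
3. If off-drug scores are not collected, remove the treatment-policy label and describe item 2 as an MMRM under MAR without imputation.

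The cost is a few already scheduled visits, for patients who stop early and agree to attend, plus footnote wording and a small SAP edit. The SAP already reports a death in the study, so conduct is advanced. If visits can no longer be added, step 3 and the handling rule in step 2 remain available before unblinding.

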# LIST OF ABBREVIATIONS AND DEFINITIONS OF TERMS

The following abbreviations and specialist terms are used in this study protocol.

Abbreviation or Specialist Term	Explanation
β-hCG	β-human chorionic gonadotropin
5-HT	serotonin
ADHD	attention-deficit/hyperactivity disorder
AE	adverse event
AESI	adverse event of special interest
ALP	alkaline phosphatase
ALT (SGPT)	alanine aminotransferase (serum glutamic-pyruvic transaminase)
aPTT	activated prothrombin time
AST (SGOT)	aspartate aminotransferase (serum glutamic-oxaloacetic transaminase)
ATRQ	Antidepressant Treatment Response Questionnaire
AUC	area under the curve
BMS	Bristol-Myers Squibb
BP	blood pressure
BUN	blood urea nitrogen
CGI-I, -S	Clinical Global Impressions Scale-Improvement, -Severity
CI	confidence interval
CK	creatine kinase
CLIA	Clinical Laboratory Improvement Amendments
$C_{\text{max}}$	maximum (peak) plasma drug concentration
СМН	Cochran-Mantel-Haenszel
CNS	central nervous system
СРК	serum creatine phosphokinase
CRO	contract research organization
CV	curriculum vitae
C-SSRS	Columbia-Suicide Severity Rating Scale
DESS	Discontinuation-Emergent Signs and Symptoms (scale)
DGM4	Denovo Genomic Marker 4, a genetic biomarker for DB104 (liafensine)
DILI	drug-induced liver injury
DNA	deoxyribonucleic acid
DSM-5	Diagnostic and Statistical Manual of Mental Disorders, 5 th Edition
ECG	electrocardiogram
eCRF	electronic Case Report Form
EDC	electronic data capture (system)

Abbreviation or Specialist Term	Explanation
EOT	End-of-Treatment
FAS	Full Analysis Set
FDA	(United States) Food and Drug Administration
FT 3	free triiodothyronine
FT 4	free thyroxine
GCP	Good Clinical Practice
HAMD-17	Hamilton Depression Rating Scale - 17 Item
HBsAg	hepatitis B surface antigen
HCV	hepatitis C virus
HIPAA	Health Insurance Portability and Accountability Act
HIV	human immunodeficiency virus
IB	Investigator's Brochure
ICH	International Council for Harmonisation of Technical Requirements for Pharmaceuticals for Human Use
ICF	informed consent form
IDMC	Independent Data Monitoring Committee
IEC	Independent Ethics Committee
IgM	immunoglobulin M (antibodies)
IMP	investigational medicinal product
IRB	Institutional Review Board
IRT	Interactive Response Technology
IVD	in vitro diagnostic
LS	least-squares
MAD	multiple ascending dose
MADRS	Montgomery-Åsberg Depression Rating Scale
MAOI	monoamine oxidase inhibitor
MCH(C)	mean corpuscular hemoglobin (concentration)
MCV	mean corpuscular volume
MDD	major depressive disorder
MDMA	3,4-methylenedioxy-N-methylamphetamine ("Ecstasy")
(MGH) ATRQ	(Massachusetts General Hospital) Antidepressant Treatment Response Questionnaire
MINI	Mini International Neuropsychiatric Interview
NMDA	N-methyl-D-aspartate
PCI	potentially clinically important
PGx	pharmacogenomics

Abbreviation or Specialist Term	Explanation
PI	principal investigator The investigator who leads the study conduct at an individual study center. Every study center has a principal investigator.
PK	pharmacokinetic
PRDF	Patient Rated Depression and Functioning (Checklist)
PRPS	Placebo Response Propensity Scale
SAD	single ascending dose
SAP	statistical analysis plan
SDS	Sheehan Disability Scale
SNP	single nucleotide polymorphism
QD	once daily
QTcF	corrected QT interval measurement according to the Fridericia rule
RBC	red blood cell (count)
REMS	Risk Evaluation and Mitigation Strategy
SAE	serious adverse event
SNP	single nucleotide polymorphism
SNRI	serotonin norepinephrine reuptake inhibitor
SOA	schedule of assessments
SSRI	selective serotonin reuptake inhibitor
SUSAR	suspected unexpected serious adverse reactions
TBL	total bilirubin
TCA	tricyclic antidepressants
TEAE	treatment-emergent adverse event
TRD	treatment-resistant depression
TSH	thyroid-stimulating hormone
UDS	urine drug screen
ULN	upper limit of normal
US	United States
WBC	white blood cell (count)

